10.2. ENDPOINT DEFINITIONS

10.2.1. PRIMARY ENDPOINT

The proportion of study participants alive and progression free at 6 months (day 1 week 25 visit). Progression will be measured from the date of study entry (registration date) until the first date of either death or confirmed progressive disease according to RECIST. Patients alive and free from progression will be censored at the date of last follow-up. The proportion of patients progression free at 6 months will be reported with 95% confidence interval. In addition, progression free survival will be presented using the Kaplan Meier product limit method with median progression free survival reported.

A blinded central review of CT scans will be conducted for verification purposes.

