7.8. PROCEDURE IF PATIENT IS WITHDRAWN FROM AXITINIB TREATMENT

- CT thorax, abdomen and pelvis and assessment of response according to RECIST 1.1 criteria prior to commencement of any subsequent treatment

7.9. PROCEDURE AT DISEASE PROGRESSION:

Axitinib therapy should be continued until there is clinically significant disease progression, after which treatment should be discontinued and the following investigations should be conducted.

- Physical examination including ECOG performance status, body weight, temperature, blood pressure, heart rate, respiratory rate
- Haematology, coagulation, glucose, renal and liver function, serum calcium and LDH
- Toxicity assessment (NCI CTCAE v.4)
- CT thorax, abdomen and pelvis and assessment of response according to RECIST 1.1 criteria prior to commencement of any subsequent treatment
- Blood samples and urine sample for biomarker analysis (see Appendix B)
- Biopsy of site of progression, or if not possible, percutaneous primary tumour biopsy via appropriate (US or CT) guidance (see Appendix B), one week after stopping axitinib treatment. Biopsy should be taken prior to commencement of any subsequent treatment.
- Assessment of concomitant medications

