7.11. FOLLOW UP

Patients should be followed up for survival and performance status every 12 weeks after treatment discontinuation.

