7.13. SCHEDULE OF ASSESSMENTS

Visit/Assessment	Up to 21 days Pre-registration	Pre-treatment day 1 week 1*	Day 1 week 3	Day 1 week 5	Day 1 Week 8	Day 1 week 9	Day 1 week 13	Day 1 week 17	Day 1 week 21	Day 1 week 25#	Disease progression
Confirmation of histological diagnosis of metastatic renal cell carcinoma	X										
Medical history	X										
Physical examination including ECOG performance status, body weight, height, temperature, blood pressure ⁷ , heart rate, respiratory rate	X	X	X	X		X	X	X	X	X	X
Haematology, coagulation, glucose, renal and liver function, serum calcium and LDH	X	X		X		X	X	X	X	X	X
Urinalysis for protein	X	X		X		X	X	X	X	X	
Symptom assessment (NCI CTCAE v.4)	X	X	X	X		X	X	X	X	X	X
Serum Thyroid Function Tests (Free T4 and TSH)	X		X	X			X ⁴		X		
Pregnancy test (serum or urine) if applicable	X										
CT thorax, abdomen and pelvis and tumour assessment using RECIST 1.1 criteria	X ¹					X		X		X ⁵	X
Percutaneous image guided biopsy of non-necrotic region of primary renal tumour and possibly one metastatic site (see Appendix B)	X ²					X					X ⁶
Blood samples and urine sample for biomarker analysis (Appendix B)		X				X					X
Assessment of compliance with study medication			X		X	X	X	X	X	X	
Dispense axitinib		X		X		X ³	X	X	X	X	
Stop axitinib 5-7 days prior to biopsy					X						
Assessment of concomitant medications	X	X	X	X		X	X	X	X	X	X

• * Day 1 week 1 assessments may be omitted if conducted within previous 7 days as part of pre-registration assessments (apart from pregnancy test)

• # Subsequent visits to take place 4 weekly thereafter to six years, after which they should take place 12 weekly.

1. CT thorax, abdomen and pelvis should be conducted prior to biopsy
2. One week prior to starting axitinib if possible.
3. Patient to restart axitinib 2-3 days after biopsy
4. Subsequent thyroid function tests should be conducted every 8 weeks to six years, after which they should be conducted 12 weekly
5. Subsequent tumour imaging to be performed 12 weekly thereafter and at treatment discontinuation/progression
6. Biopsy of site of progression, or if not possible, percutaneous image guided primary tumour biopsy. Biopsy should be taken prior to commencement of any subsequent treatment.

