8.4. DOSE INTERRUPTION AND REDUCTION

Patients experiencing non-haematological drug reactions greater than CTCAE Grade 2 or haematological reactions greater than CTCAE Grade 3 should undergo dose modification. The current version of the SmPC should be used to assess whether any adverse event is attributable to the drug.

Axitinib should be stopped in the event of significant toxicity and restarted if appropriate when toxicities have resolved. Recovery to acceptable levels of toxicity must occur within 4 weeks to allow recommencement of treatment.

Patients permanently removed from treatment for intolerable toxicity should receive a post treatment CT scan assessed according to RECIST 1.1 criteria, and should continue to be followed with regular tumour assessments until disease progression or start of new treatment, and for survival thereafter.

The criterion for dose modification for axitinib related adverse events is summarised in the table below:

8.4.1. CRITERIA FOR DOSE MODIFICATION FOR AXITINIB - RELATED ADVERSE EVENTS (OTHER THAN HYPERTENSION OR PROTEINURIA)

Related Adverse Events	INTERVENTION
Any Grade: Bleeding where medical intervention is required	Temporarily interrupt the axitinib dose.
Any Grade: Posterior reversible encephalopathy syndrome (PRES)	Patients with signs or symptoms should temporarily interrupt or permanently discontinue axitinib treatment. In case of severe or persistent arterial hypertension and symptoms suggestive of posterior reversible encephalopathy syndrome, a diagnostic brain magnetic resonance image (MRI) should be considered.
Moderate hepatic impairment (Child-Pugh class B)	A dose decrease is recommended
Grade 1 or 2	Continue at same dose level
Grade 3 non-haematologic treatment-related toxicity	Decrease dose to one lower dose level unless controlled with symptomatic medications.
Grade 3 asymptomatic biochemistry laboratory abnormalities	Continue at the same dose level at the discretion of the investigator
Grade 4 non-haematologic treatment-related toxicity or Grade 4 haematologic toxicity (other than those below)	Interrupt dosing; re-start at one lower dose level as soon as improvement to CTCAE Grade ≤2. If patient requires dose reduction below 2 mg BID, contact ICR-CTSU for discussion prior to implementation.
Grade 4 lymphopaenia or Grade 4 asymptomatic biochemistry laboratory abnormality	Continue at the same dose level at the discretion of the investigator

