8.9. DURATION OF THERAPY

In the absence of unacceptable toxicity treatment should continue until the patient is no longer deriving clinical benefit.

Patients may also discontinue protocol treatment in the following instances:

- Intercurrent illness which would in the judgment of the investigator affect patient safety, the ability to deliver treatment or the primary study endpoints
- Request by patient

Patients for whom treatment is discontinued should be followed for disease progression and for survival thereafter according to the Schedule of Assessments (see section 7).

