10.2.2. SECONDARY ENDPOINTS

Best overall response is defined as the best tumour response that is achieved during or within 30 days after termination of axitinib that is confirmed according to RECIST.

Progression-free survival (PFS) will be measured from the date of registration until first date of either death or confirmed progressive disease according to RECIST 1.1. Time to last follow-up will be used if patient has not progressed or died and PFS time for the patient will be considered censored. A Kaplan Meier graph and median survival time will be presented.

Overall survival will be measured from the date of registration until the date of death due to any cause. Time to last follow-up will be used if patient has not died and survival time for the patient will be considered censored. A Kaplan Meier graph and median survival time will be presented.

Safety and toxicity will be assessed throughout the treatment period using the NCI CTC AE v 4.0 and summarised in tabular format. Reported toxicities will be coded using MedDRA (current version).

The proportion of patients who undergo nephrectomy following registration as a result of treatment with axitinib will be reported with 95% confidence intervals.

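### PFS is censored at last follow-up, the same date as for OS, and is not tied to a tumour assessment; read literally, this biases the Kaplan-Meier PFS curve slightly upward

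*Combined protocol and SAP*

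**What the plan says.** **Censoring.** Section 10.2.1: "Patients alive and free from progression will be censored at the date of last follow-up". For PFS as a secondary endpoint, 10.2.2 has: "Time to last follow-up will be used if patient has not progressed or died". For OS the same section has: "Time to last follow-up will be used if patient has not died and survival time for the patient will be considered censored". Neither section defines last follow-up or links it to a scan.

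**What follow-up consists of after axitinib stops.**
- 7.11: "Patients should be followed up for survival and performance status every 12 weeks after treatment discontinuation".
- 8.4, for patients stopped for toxicity: they "should continue to be followed with regular tumour assessments until disease progression or start of new treatment, and for survival thereafter".
- 8.9: "Patients for whom treatment is discontinued should be followed for disease progression and for survival thereafter according to the Schedule of Assessments".
- 7.8, at withdrawal from treatment: CT and "assessment of response according to RECIST 1.1 criteria prior to commencement of any subsequent treatment".
- 7.13, footnote 5: "Subsequent tumour imaging to be performed 12 weekly thereafter and at treatment discontinuation/progression". The table has no column for visits after discontinuation.
- 7.7: the heading runs the four-weekly visits to six years or progression, with CT at weeks 17 and 25 and 12-weekly afterwards.
- 18.7 asks sites to try to document objective progression after treatment has stopped.

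**Related analysis.** Section 10.3 plans a Kaplan-Meier sensitivity analysis that censors withdrawals, but gives no censoring date.

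**The concern.** OS can properly be censored at the last date the patient was known to be alive, because any contact can establish that. RECIST progression can be established only by a tumour assessment. If the PFS censoring date may be a contact for survival only, the time between the last scan and that contact enters the risk set as progression-free time when progression could not have been seen. A patient who progresses unscanned in that interval appears as censored late, or as an event at death instead of at progression. Both push the curve up.

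The PFS curve and median are to be presented with the primary endpoint and again as a secondary endpoint. They will be read against outside figures, such as the 5.5-month median PFS that the protocol cites for temsirolimus.

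**Working it through.** **1. Decision rule (10.1).** Success probability is Σ over x = 11…37 of Bin(x; 37, p) × P(X₂ ≥ 32 − x), with X₂ ~ Bin(62, p). This gives 0.0493 at p = 0.25 and 0.9002 at p = 0.40, matching the stated one-sided 0.05 and 90% power. The inputs are counts at 6 months, and no censoring date enters.

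**2. Who is exposed.** Under 8.4, a patient stopped for toxicity who starts new treatment without progression has survival follow-up only from then on. The literal rule clearly carries that patient forward as progression-free. Between stopping and new treatment, 8.4 and 8.9 call for progression follow-up while 7.11 names none, so exposure there depends on which section the site follows.

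**3. Size at 12 months, by hand.** The documents give no rate of stopping or of missed scans, so these are assumptions: exponential PFS with 6-month PFS of 40%; 10% of patients stop before month 6 without an event; unscanned stoppers are seen only at death, with a median of 10.9 months (the OS median quoted in section 1.3).
- Progression or death: λ = −ln(0.40)/6 = 0.1527 per month, so true S(12) = 0.40² = 0.160.
- Death only: μ = ln 2/10.9 = 0.0636 per month.
- For a patient who stops unscanned at month s, the excess at 12 months is exp(−μ(12 − s)) − exp(−λ(12 − s)). At s = 3 this is 0.564 − 0.253 = 0.311; at s = 6 it is 0.683 − 0.400 = 0.283.
- Half of stoppers unscanned: 0.10 × 0.5 × 0.311 = 0.016, or 1.6 points.
- One in ten unscanned: 0.10 × 0.1 × 0.311 = 0.003, or 0.3 points.
- If stopping continues at the same rate after month 6, these become about 1.9 points (17.9%) and 0.4 points (16.4%).

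**4. Size with stopping linked to prognosis.** Simulation with 2 million patients per case, 10% stopping before month 6, half of stoppers unscanned; 12-month PFS:

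| Case | True | Last follow-up | Last scan, deaths kept |
|---|---|---|---|
| (i) Stopping unrelated to prognosis | 16.0% | 17.9% | 16.2% |
| (ii) Progression hazard doubles after stopping | 15.1% | 18.2% | 16.5% |
| (iii) Progression and death hazards both double | 15.1% | 16.7% | 15.9% |

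The upward bias is 1.9, 3.1 and 1.6 points for last follow-up, and 0.2, 1.4 and 0.8 points for last scan. Changing how stopping times are drawn keeps the first set at roughly 1.3 to 3 points.

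**5. Median.** Progression is dated at scans, here 16 weeks (3.68 months) and 24 weeks (5.52 months) after the start. With λ as above, S = 0.570 and 0.430 at those dates. The literal rule adds at most 0.05 × 0.274 = 0.014 at 24 weeks (stopping at time 0), giving 0.444. The curve crosses 50% at the same scan, so the median reads 5.52 months either way. A continuous-time model shows a shift from 4.54 to 4.63 months, but that is not how progression will be dated.

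**6. Patients still on treatment.** Four-weekly visits fall between 12-weekly scans, so last follow-up can also postdate the last scan here. With administrative censoring only and 0, 15 or 30% of events being deaths, week-48 PFS is 15.97, 15.98 and 15.96% without censoring; 15.97, 15.92 and 15.86% censoring at last visit; and 15.97, 15.82 and 15.67% at last scan. There is no upward bias from this source.

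**The case against.** **Progression follow-up after stopping is required.** This largely stands. Section 7.7 runs visits to progression, not to the end of treatment. Sections 7.8, 8.4, 8.9 and 18.7 all call for assessment after stopping, and footnote 5 of 7.13 can be read as adding a scan at discontinuation. A reader might infer that progression cannot be recorded at all once axitinib stops; the documents do not support that. What remains is time after new treatment, and time before it if a site works from 7.11 alone.

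**Last follow-up is undefined, so the bias is one permitted reading.** This is true. A statistician could take it as the last tumour assessment. But 10.2.2 uses the same words for OS, where any contact counts, so the literal reading is a natural one and should be closed off.

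**Section 10.3 already censors withdrawals in a sensitivity analysis.** This partly covers the exposed group. Without a stated date, it could carry the same problem.

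**The effect is small.** This is also true. With 99 patients, the standard error near 16% is about √(0.16 × 0.84/99) = 3.7 points, larger than the bias in any case in the table.

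**The trial's conclusion might seem at risk.** A reader might infer that the censoring date inflates the 11/37 and 32/99 counts. It does not, because those are counts of patients at 6 months. PFS as a curve and median is descriptive, with no test attached.

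**Conclusion.** The point holds in limited form. The PFS censoring date is not tied to a tumour assessment. Taken literally, it extends progression-free time through contacts that cannot detect progression, clearly so after new treatment starts. With about 10% of patients stopping before month 6, the upward bias at 12 months is about 0.3 to 0.5 points if one stopper in ten is unscanned and about 1.3 to 3 points if half are. The second case presumes wide departure from 8.4 and 8.9. All these rates are assumptions; the direction does not depend on their exact values.

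The documents do not support a claim that the median is biased. On the scan grid, under these assumptions, it stays at the same scan date. It could shift only if the true curve lay just below 50% at a scan. Nor is the decision rule affected.

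A separate and minor matter is that 18.6 labels a patient without imaging as not evaluable, and no section assigns such a patient, alive at week 25, to the counts. A reader might infer that these patients inflate the 6-month proportion. Section 10.1 points the other way: it counts out of all patients entered and speaks of patients observed to be event-free. The status is unassigned, and no inflating rule is stated.

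**What to change.** 1. In 10.2.1 and 10.2.2, censor patients without progression or death at the last evaluable RECIST assessment, and keep deaths as events. Use the same date in the 10.3 analysis that censors withdrawals. Keep censoring at last follow-up as a sensitivity analysis.
2. Reconcile 7.7, 7.11, 8.4, 8.9 and footnote 5 of 7.13 on tumour assessment after discontinuation, so that sites work from one instruction.
3. As a minor clarification, state before the 11/37 and 32/99 counts are made how a living patient not evaluable at week 25 is counted, with the alternative as a sensitivity analysis.

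**Cost.** Items 1 and 2 are wording, and item 1 leaves the decision rule and its power unchanged. Last-scan censoring is not unbiased when stopping is linked to prognosis (16.5% against a true 15.1% in case ii). For patients still on treatment it reads up to 0.3 points low at 48 weeks if 30% of events are deaths.

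Item 3 matters at the margin because 31 fails and 32 passes. If not evaluable counts as not progression-free, and 2.5% of all patients are progression-free but unassessed, the effective rate is 0.40 − 0.025 = 0.375 and power falls from 0.900 to 0.807. If such patients count as successes, and 1% of all patients are unassessed progressors, the success probability at a true 25% rises from 0.049 to 0.077. Both shares are assumptions.

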10.2.2. SECONDARY ENDPOINTS

Best overall response is defined as the best tumour response that is achieved during or within 30 days after termination of axitinib that is confirmed according to RECIST.

Progression-free survival (PFS) will be measured from the date of registration until first date of either death or confirmed progressive disease according to RECIST 1.1. Time to last follow-up will be used if patient has not progressed or died and PFS time for the patient will be considered censored. A Kaplan Meier graph and median survival time will be presented.

Overall survival will be measured from the date of registration until the date of death due to any cause. Time to last follow-up will be used if patient has not died and survival time for the patient will be considered censored. A Kaplan Meier graph and median survival time will be presented.

Safety and toxicity will be assessed throughout the treatment period using the NCI CTC AE v 4.0 and summarised in tabular format. Reported toxicities will be coded using MedDRA (current version).

The proportion of patients who undergo nephrectomy following registration as a result of treatment with axitinib will be reported with 95% confidence intervals.

10.2.3. EXPLORATORY ENDPOINTS

Analysis of response by biomarker sub-group will be descriptive in nature. Fisher's Exact Tests are likely to be reported, however, they will only be used for hypothesis generation due to the limited power of the study. Correlation between biomarker sub-groups and reported toxicity will also be explored via interaction tests. A false discovery rate of <5% will be applied to all biomarkers.

CT scans collected for central verification of the primary endpoint will be used to determine the extent of venous tumour thrombus in the IVC for each participant and the effect of axitinib treatment on VTT. The primary objective of this exploratory analysis will be to establish the proportion of patients with a reduction in Neves' classification (level of the VTT within the IVC) [30]. Secondary objectives will be to assess the height of the VTT above the ostium of the renal vein/IVC in this patient population and change in texture of IVC VTT following treatment with axitinib.

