2.3. EXPLORATORY OBJECTIVES

The exploratory objectives of this study are to:

- correlate changes in biomarkers with toxicity, response to treatment and survival.

- investigate any effect of treatment on the extent of inferior vena cava (IVC) venous tumour thrombus (VTT)

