10. STATISTICAL CONSIDERATIONS

10.1. STATISTICAL DESIGN AND SAMPLE SIZE JUSTIFICATION

This study is designed to assess the efficacy of axitinib in patients with mRCC not immediately clinically indicated for nephrectomy, a very poor risk group of patients. The median progression free survival for poor risk patients with mRCC treated with temsirolimus, the standard of care in this setting, is approximately 5.5 months[17]. Some benefit is expected for patients treated with axitinib, but the

expected degree of benefit is not known, nor is it known whether there will be a benefit via an increased response rate, or a prolongation of response, or both, detectable in PFS at 6 months.

Using a Simon Optimal Two-Stage design this study has 90% power at a one-sided significance level of 0.05 to discount an 'ineffective' rate of freedom from progression at 6 months (PFS6) of 25% (p_0) in favour of a PFS6 of at least 40% (p_1). This point estimate (40%) is lower than perhaps expected for temsirolimus (ignoring the inevitable variability around these estimates). However, a slightly lower threshold for axitinib may be acceptable given it is well tolerated and an oral compound, thus requiring fewer visits to hospital than for an IV drug such as temsirolimus.

37 patients will be treated in stage one and, if successful, a further 62 patients in stage two bringing the total number of patients required to 99. There will be no planned stopping in recruitment between stages 1 and 2; patients will be entered into stage 2 whilst stage 1 patients are progressing through the trial, their data being analysed and reviewed by the Independent Data Monitoring and Steering Committee (IDMSC).

The trial will stop and the treatment will be rejected if there are fewer than 11 patients alive and progression free at 6 months when the first 37 patients have been on trial for 6 months. If 11 or more of the first 37 patients are alive and progression free at 6 months a further 62 patients will be recruited into the second stage. If there are 32 or more patients of the overall 99 entered alive and progression free at 6 months axitinib will be considered to have shown worthwhile efficacy, but not if there are 31 or less. Planning for a phase III trial can commence at any stage if 32 patients have been observed to be alive and progression free at 6 months. No data will be released from stage 1 whilst recruitment to stage 2 is ongoing unless advised to do so by the IDMSC.

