19.7.3. DATA ANALYSIS OF GENETIC HIGH-THROUGHPUT METHODS

The data from the high-throughput methods described above will be analysed by the bioinformatics group at the Francis Crick Institute. Pre-treatment expression signatures and changes in expression levels on treatment will be correlated with clinical response, primary resistance and to the development of secondary resistance to axitinib treatment as assessed by CT scanning. Gene specific quantitative rtPCR analyses will be used to validate expression data from the high-throughput assays and to correlate findings from whole genome RNAi analyses performed in renal cancer models *in vitro*.

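### Section 10.2.3 analyses biomarkers by sub-group with Fisher's exact test, but many planned markers are quantitative; analysing those uncut would keep more of the limited power

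*Combined protocol and SAP*

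**What the plan says.** The exploratory objective in section 2.3 is to "correlate changes in biomarkers with toxicity, response to treatment and survival". Section 10.2.3 turns this into an analysis plan. Response is examined by biomarker sub-group and described as descriptive. Fisher's "Exact Tests are likely to be reported, however, they will only be used for hypothesis generation due to the limited power of the study". Toxicity is also related to biomarker sub-groups, through interaction tests. On multiplicity, "A false discovery rate of <5% will be applied to all biomarkers". The section does not say how sub-groups are formed, names no method that keeps a marker on its measured scale, and names no method for biomarkers against survival.

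Appendix B goes a little further for expression data. Section 19.7.1 compares expression patterns between patients who respond, stabilise or progress. Section 19.7.3 adds that "changes in expression levels on treatment will be correlated with clinical response". Neither names a test or model. Section 19.8 describes ELISA measurement of plasma proteins and quantification of circulating tumour DNA, but not how either will be related to outcome.

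**The concern.** Fisher's exact test on sub-groups suits a marker that is already categorical. A plasma concentration, a circulating tumour DNA amount or a change in expression is not, and someone must choose a cut before it can enter the analysis 10.2.3 describes. Cutting discards the ordering within each group, and Fisher's test is conservative in small tables. Both losses fall on an analysis whose limited power the plan already concedes.

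Section 19.1 presents the evaluation of biomarker change as a key aim, and patients have a baseline biopsy, a week 9 biopsy with treatment paused, and a biopsy at progression to support it. A hypothesis-generating analysis that misses real associations loses much of what those samples could give.

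**Working it through.** **The plan's own figure.** Section 10.2.3 gives no effect size, cut-point, evaluable number or power, so there is no biomarker figure to reproduce. The primary design in section 10.1 supplies the upper limit on patients and can be checked. It claims "90% power at a one-sided significance level of 0.05" for 25% against 40%. "37 patients will be treated in stage one and, if successful, a further 62 patients in stage two"; the trial stops with "fewer than 11 patients alive and progression free at 6 months", and success needs at least 32 of 99.

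P(success | p) = sum over x = 11 to 37 of b(x; 37, p) × P[Bin(62, p) ≥ 32 − x]

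- p = 0.25: 0.0493
- p = 0.40: 0.9002

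The design reproduces. Nothing below touches it.

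**Which markers have a stated method outside 10.2.3?**

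| Marker | Scale | Method stated elsewhere |
|---|---|---|
| RNA and miRNA expression, and changes (19.7.1, 19.7.3) | quantitative | compared or correlated without grouping; no test named |
| Plasma VEGF, PlGF, sVEGFR1-3 (19.8) | quantitative | none |
| Circulating tumour DNA amount (19.8) | quantitative | none |
| Sequence findings before and after treatment (19.7.2) | categorical | none, but Fisher's test is suitable |

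**Cost of grouping, first model.** Assumptions, none of them in the documents: a standard normal marker; logit P(response) = a + ln(2.0) × marker, with a set to give 30% response overall; a median split for Fisher's test; and a Mann-Whitney test on the same data uncut. The protocol does not say how many patients will have usable samples, so n = 60 and 80 are shown beside the maximum of 99.

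| n | Two-sided threshold | Fisher, median split | Rank test | Difference (points) |
|---|---|---|---|---|
| 60 | 0.05 | 35% | 59% | 24 |
| 80 | 0.05 | 46% | 73% | 27 |
| 99 | 0.05 | 61% | 81% | 20 |
| 99 | 0.005 | 29% | 50% | 21 |

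With 3,000 simulated trials the standard error is at most √(0.25/3000) = 0.9 points, so these figures are good to about two points. With no association and a nominal 5% level, Fisher's test rejects about 3% of the time at n=80 and about 4% at n=99.

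**Second model.** The marker is shifted by d SD in responders, the number of responders is fixed, and 4,000 trials are simulated per setting. At n = 99 and two-sided 5%:

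| Response rate | d | Fisher, median split | Mann-Whitney | t-test |
|---|---|---|---|---|
| 40% | 0.5 | 51% | 66% | 68% |
| 40% | 0.6 | 66% | 81% | 84% |
| 40% | 0.8 | 88% | 96% | 97% |
| 25% | 0.5 | 42% | 54% | 57% |
| 25% | 0.6 | 57% | 72% | 74% |
| 25% | 0.8 | 79% | 92% | 93% |

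Over d = 0.5 to 0.8 the loss against the rank test is about 8 to 15 points. An upper-quartile cut is worse: 54% against 81% for the rank test at 40% response and d = 0.6.

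**Where the loss comes from.** The large-sample efficiency of a median split is 2/π = 0.64, so 99 patients act like 99 × 0.64 ≈ 63. At n = 99 in the second model, Fisher's test and an uncorrected chi-square on the same split have practically the same power, so the loss is from cutting. At n = 60 (40% response, d = 0.6) the powers are Fisher 27%, chi-square 48% and rank test 57%. There, about 9 points come from cutting and 21 from the conservatism of Fisher's test.

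**The case against.** The strongest reply is that 10.2.3 commits to very little. The sub-group analysis is descriptive, the tests are only likely, and their use is confined to hypothesis generation. The documents nowhere mention a cut-point, and sub-groups could simply be mutation-defined, for which Fisher's test is right. Sections 19.7.1 and 19.7.3 already describe uncut analysis of expression data.

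Much of this stands. Four stronger readings are tempting, and the documents do not support them:

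- **That the trial has committed to dichotomising its markers.** The wording is provisional and not exclusive, and cutting is inferred from the word sub-group.
- **That all biomarker changes are continuous.** Section 19.7.2 looks for candidate genes before and after treatment, and a gained or lost mutation is categorical.
- **That cut-points will be picked after seeing the data, inflating false positives.** No rule is given either way, so this is speculation.
- **That one false discovery rate family will let genome-wide features swamp the named markers.** The phrase "A false discovery rate of <5% will be applied to all biomarkers" does not define the family and could equally mean control within each assay. The number of features is not stated either. The family would be worth clarifying, but the present point does not rest on it.

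A further fair objection is that power at 5% per marker is not power under the plan's false discovery rate rule. At 0.005, Fisher's test against the rank test gives about 11% against 26% at n=60 and 17% against 38% at n=80. If 20,000 features in one family were assumed, the first-rank threshold would be 0.05/20,000 = 2.5e-6, and both tests would have under 2% power. Uncut analysis therefore does not make the study well powered. At 5% and 0.005 it is clearly better than the named alternative.

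The reply leaves one gap open. For plasma proteins and circulating tumour DNA, 10.2.3 is the only statement of how a marker meets outcome, and it offers only sub-groups.

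**Conclusion.** The point holds as a cheap improvement. Section 10.2.3 should not leave a sub-group analysis with Fisher's exact test as the only named route to response for markers measured on a continuous scale. Under the first model a median split with Fisher's test gives up roughly 20 to 27 points of power against a rank test; under the second, about 8 to 15 points at n = 99. The size depends on the assumed normal marker, effect size, response rate, split and evaluable number, none of which the documents supply. The direction was the same in every setting tried at the 5% and 0.005 thresholds. Truly categorical markers are unaffected. The endpoint is exploratory, stored measurements can be analysed either way, and the primary decision rule does not change.

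**What to change.** In section 10.2.3:

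- Analyse quantitative markers and their changes uncut: a rank test or logistic regression for response and toxicity, and Cox regression for progression-free and overall survival.
- Reserve Fisher's exact test for truly categorical markers, such as mutation present or absent.
- Show any table based on a cut-point as description only, and state how its groups were formed.
- Align the wording with 19.7.3, so that the statistical section and Appendix B describe the same analysis, and make clear that it also covers the plasma proteins and circulating tumour DNA of 19.8.

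The cost is wording: no new samples, visits or data. There is slightly more analysis work, and the regression versions assume linearity on the chosen scale, which should be checked; the rank test avoids that assumption. In Cox models of week 9 changes, follow-up time should be counted from the week 9 sample.
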